7.1.2 Secondary Efficacy

The secondary efficacy endpoint is to evaluate the effect of daily Collagenase Santyl ointment versus daily Bacitracin ointment on scar appearance at 90 days and at 180 days after the initiation of treatment. The secondary efficacy endpoint is defined as the VSS total score obtained at Visit 7 (Day 90) and at Visit 8 (Day 180).

The treatment effect of Collagenase Santyl ointment versus Bacitracin ointment on the VSS total scores will be obtained at each of the two post-healing assessment time points, using analysis of variance (ANOVA) for the ITT population. The mixed-effect model will utilize SPSSPROC MIXED to perform the analysis and define treatment (Santyl vs. Bacitracin) and assessment time point (4 visits: Visits 5, 6, 7 and 8) as well as their interaction as fixed effects, and subject as a random effect. The option of variance components will be used to define the covariance structure of the model.

In addition, a model-based t-test comparisons between Santyl vs. Bacitracin will be performed for each of the 2 assessment time points (or visits).

The null hypothesis states that there are no differences between the two treatments, with the alternative of non-zero differences. The type I error rate for rejecting a null hypothesis will be set at an alpha level of 0.05.

Prior to conducting the analysis, those VSS total scores that are obtained at the early termination visit will be assigned to the next scheduled study visit.

The analyses of the primary efficacy evaluations will also be performed for the PP population.

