7. STATISTICAL DESIGN

7.1 EVALUABILITY

All subjects who receive study medication will be evaluable for the safety analysis. All subjects who are randomized to receive study medication will be evaluable for the intent-to-treat analysis.

Unless specified otherwise, SPSS® Version 10.0 or higher will be utilized to perform the statistical analyses of efficacy and safety measures.

Categorical variables will be summarized in general using frequencies and percentages, whereas continuous variables will be summarized in general using descriptive statistics of number of observations (n), mean, standard deviation (SD), minimum (Min), median, and maximum (Max).

Hypothesis testing, unless otherwise indicated, will be performed at the 5% significance level. All P values will be rounded to four decimal places; P values less than 0.0001 will be presented as '<0.0001' in all tables. All group comparisons from analysis of variance (ANOVA) and/or analysis of covariance (ANCOVA) models will be based on Type III sums of squares. All confidence intervals will be two-sided with 95% coverage.

Missing or invalid data of efficacy assessments will be handled by individual scales or subscales on the basis of each individual assessment. Missing data for individual items will be assessed for each assessment of each scale and imputed with the mean score of the corresponding assessment and rounded up to the nearest integer if the number of items with missing data or invalid is less than or equal to 20% of total item number. Otherwise, the assessment score will be set to missing.

Considering that a subject's burn wound may be healed and/or a subject may discontinue from the study prior to the end of the study period, missing values at each weekly visit due to either burn wound healing or early termination or any other reasons will be imputed in this study prior to deriving the efficacy endpoints for evaluation, using the technique of last-observation carried forward (LOCF). By so doing, a burn wound that heals sooner will be given more weight for efficacy.

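### Section 7.1.2 tests the VSS score at two unranked visits with overlapping analyses, each at 0.05, so the chance of a false significant scar result is about 8% to 14%, not 5%

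*Combined protocol and SAP*

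**What the plan says.** Section 7.1.2 (Secondary Efficacy) defines one secondary endpoint at two time points: the VSS total at Visit 7 (Day 90) and at Visit 8 (Day 180). It states a single two-sided hypothesis, "no differences between the two treatments, with the alternative of non-zero differences", and then describes three pieces of analysis:

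- The treatment effect "will be obtained at each of the two post-healing assessment time points, using analysis of variance (ANOVA) for the ITT population".
- A mixed model with treatment, "assessment time point (4 visits: Visits 5, 6, 7 and 8) as well as their interaction as fixed effects", and subject as a random effect. On the covariance: "The option of variance components will be used to define the covariance structure of the model".
- As an addition, "a model-based t-test comparisons between Santyl vs. Bacitracin will be performed for each of the 2 assessment time points".

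On error control, section 7.1.2 says: "The type I error rate for rejecting a null hypothesis will be set at an alpha level of 0.05". Section 7.1 gives the general rule: "Hypothesis testing, unless otherwise indicated, will be performed at the 5% significance level". Neither section says which analysis or visit decides the scar conclusion, and neither adjusts for the number of tests.

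**The concern.** One question, whether scars differ between the arms, can be answered by several p-values. Each is judged at 0.05, and any of them could be reported as the scar result. If the tests disagree, the plan does not say which one stands.

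Scar appearance is the only secondary endpoint, and the background in section 2.1 gives scar reduction as a motive for the study. The synopsis marks blinding as none, which is a further reason to fix the deciding analysis before the data are seen. A reader of a positive scar result could not tell whether it came from the test that was meant to count.

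**Working it through.** **Inputs from the documents.** 40 per group and effect size 0.750 (section 8); two-sided 0.05 (sections 7.1.2 and 8); two VSS visits; mixed model with a random subject effect (section 7.1.2).

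**Assumptions.** The documents give no between-visit correlation (rho), so 0.3 to 0.8 is used. Scores are taken as normal and complete, with equal SD at both visits. VSS is a bounded ordinal score, so the results are approximate.

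**Step 1: the plan's own 0.05.** A single per-visit test gave 4.95% to 5.2% in null simulations over this range of rho, as it should.

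**Step 2: two visits, one test each.** The chance of at least one false rejection is 1 − P(|Z1| < 1.96 and |Z2| < 1.96), where Z1 and Z2 have correlation rho. At rho = 0 this is 1 − 0.95² = 9.75%. The first results column below gives the values for rho 0.3 to 0.8.

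**Step 3: the analyses as listed, Visits 7 and 8** (40,000 null trials per rho). With two visits and complete data:
- The mixed-model treatment effect is a t-test on each subject's mean of the two scores.
- The interaction is a t-test on each subject's change between visits.
- The model-based t-test at a visit uses variance (MSB + MSE)/2. MSB is twice the pooled variance of subject means, and MSE is half the pooled variance of changes. The degrees of freedom are Satterthwaite's.

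| rho | Two per-visit ANOVAs (exact) | Plus overall treatment effect and model-based t-tests | Plus interaction | Mixed model only: treatment effect and two t-tests |
|---|---|---|---|---|
| 0.3 | 9.51% | 11.4% | 13.9% | 10.7% |
| 0.5 | 9.07% | 10.3% | 13.4% | 9.7% |
| 0.7 | 8.35% | 9.4% | 13.1% | 8.9% |
| 0.8 | 7.81% | 8.3% | 12.3% | 8.0% |

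**Step 4: where the excess comes from.** At rho = 0.5 the treatment comparisons exceed 5% by 10.3 − 5 = 5.3 points. Two visits alone account for 9.1 − 5 = 4.1 of these, or 77%. ANOVA and the model-based t-test at the same visit gave the same verdict in about 99% of null trials. If the interaction is counted, the excess is 13.4 − 5 = 8.4 points, and the two visits account for about half.

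**Step 5: sensitivity.**
- Treating six tests as independent would give 1 − 0.95⁶ = 26.5%. That overstates the risk, because the tests share data.
- If the Day 180 SD is 0.7 or 1.3 times the Day 90 SD (assumption), the two methods disagree at a given visit in about 3% to 4% of null trials. The rate is then 10.0% to 13.5% without the interaction and 12.9% to 15.1% with it.
- If all four visits named in the model carried VSS data, rho from 0 to 0.9 gives 7.7% to 14.0% without the interaction and 12.1% to 16.1% with it.

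**Step 6: power, for the cost of a fix.** Section 8 states about 70% power. Its own inputs (two-sample t-test, 40 per group, effect size 0.75, two-sided 0.05) give 91.2%, so the stated figure is not reproduced. About 70% would correspond to an effect size near 0.56. That is a separate matter, but the cost of adjustment depends on it. At 0.025, power is 85.5% for effect size 0.75 and about 59% for 0.56.

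**The case against.** **The mixed model may be the ANOVA.** The sentence on the mixed model follows directly on the one naming ANOVA and can be read as explaining how that ANOVA is run; section 7.1.1 itself speaks of a mixed-effect ANOVA. There would then be no separate per-visit ANOVA, and the t-tests would be contrasts from the one model. This reading is fair, so a count of six separate tests cannot be stated as fact. The excess remains: the last column of the table gives 8.0% to 10.7%.

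**The plan promises no familywise rate.** Both statements on alpha can be read as applying per test, and both days are named in the endpoint definition. This stands, and the plan does not break a promise. The gap is that one hypothesis is stated, several tests address it, and no rule links them to a conclusion.

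**An interaction is not a scar benefit.** A reader might infer that the chance of wrongly claiming that Santyl improves scars is about 13%. The documents do not support that. An interaction alone shows only that the difference changes over time, and these rates count both directions. Counting only treatment comparisons that favour Santyl gives 5.7% to 4.2% as rho goes from 0.3 to 0.8, against a one-direction benchmark of 2.5%. Inflation remains, but the figure is much smaller.

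**The endpoint is secondary.** This limits the consequence, and strict error control for secondary endpoints is partly a matter of preference. It does not remove the need to say which result counts.

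**Conclusion.** The point holds as a correction to a secondary analysis. On every reading examined, the chance of at least one false significant VSS result in either direction exceeds 5%. For Visits 7 and 8 with rho 0.3 to 0.8 it is about 8% to 11% from the treatment comparisons, whether or not the mixed model is itself the ANOVA. It reaches about 12% to 14% only if a significant interaction alone is taken as a scar finding. These figures rest on the assumed correlation, complete normal data and equal SDs.

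Two further inferences go too far. One is that listing three methods is the main fault: with equal SDs the methods almost always agree, and for the treatment comparisons the two unranked visits are the main source. The other is that VSS is established as the basis of the sample size: section 8 cites an earlier VSS result but does not say to which endpoint the 0.750 applies.

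**What to change.** In section 7.1.2:

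1. State that one mixed model is the deciding VSS analysis. Drop any separate per-visit ANOVA or label it supportive.
2. Test the model's Day 90 and Day 180 treatment differences with Holm's adjustment: the smaller p-value against 0.025 and, if that is significant, the other against 0.05. Alternatively, name one deciding visit.
3. Report the overall treatment and interaction terms as descriptive.
4. In the same edit, reconcile the visits in the model. Section 7.1.2 uses Visits 5 to 8. Section 6.2.3 and the table in section 12 place the VSS only at Visits 7 and 8. Section 6.5.5 starts it at full re-epithelialisation. Under section 6.2.2, a subject whose wound has closed skips the remaining weekly visits.

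Holm holds the error to at most 5%; simulation at rho 0.3 to 0.8 gives 4.2% to 4.9%. The cost is SAP wording and some power. Per-visit power at effect size 0.75 falls from 91.2% to 85.5% at the strictest step. If the true effect is nearer 0.56, it falls from about 70% to about 59%, part of which Holm's second step recovers. Naming one deciding visit avoids this loss but makes the other visit supportive only.

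### Section 7.1.2 puts four visits (5 to 8) in the mixed model for a scar endpoint defined at Visits 7 and 8, and moves early-termination scores to the next visit without a time window

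*Combined protocol and SAP*

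**What the plan says.** Section 7.1.2 fixes the endpoint at two visits: "The secondary efficacy endpoint is defined as the VSS total score obtained at Visit 7 (Day 90) and at Visit 8 (Day 180". Estimates of the difference between arms "will be obtained at each of the two post-healing assessment time points" by ANOVA, and model-based t-tests "will be performed for each of the 2 assessment time points (or visits". Between these statements it specifies a mixed model with treatment, visit and their interaction as fixed effects, subject as a random effect and a variance-components covariance. The visit factor in that model is "assessment time point (4 visits: Visits 5, 6, 7 and 8".

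For subjects who leave early, "those VSS total scores that are obtained at the early termination visit will be assigned to the next scheduled study visit". No time window is attached.

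On error control the section says only this: "The type I error rate for rejecting a null hypothesis will be set at an alpha level of 0.05".

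Sections elsewhere bear on what data could sit at Visits 5 and 6:

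- Section 6.2.2 makes Visits 2 to 6 weekly wound visits. VSS is not among their procedures, and a subject whose wound has closed skips the remaining weekly visits.
- Table 1 (Section 12) marks VSS under Visits 7-8 only. Section 6.2.3 sets those visits at Day 90 and Day 180 after Visit 1, each ±2 weeks.
- Section 6.5.5 has VSS scoring begin at full re-epithelialization, which can fall at a weekly visit.
- Section 7.1 says that "missing values at each weekly visit due to either burn wound healing or early termination or any other reasons will be imputed" by last observation carried forward (LOCF), with the reason that "a burn wound that heals sooner will be given more weight for efficacy".

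**The concern.** The endpoint and both sets of tests have two time points; the model meant to supply one set has four. An analyst cannot code the model without deciding what, if anything, belongs at Visits 5 and 6, and the sections that should settle this disagree. If scores from fresh scars enter, they help set the standard error used to test the Day 90 and Day 180 differences.

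The early-termination rule is a separate route by which a score taken at the wrong time enters an endpoint visit. A scar scored soon after Day 90 would count as a Day 180 scar, well outside the window that the protocol sets for that visit.

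**Working it through.** **1. The plan's own power figure.** Inputs from Section 8: 40 per group, effect 0.75 SD, two-sided 0.05, two-sample t-test. SE = √(2/40) = 0.2236 SD; 0.75/0.2236 = 3.354; power = Φ(3.354 − 1.960) = 91.8% (91.2% with the exact t). Section 8 states about 70%, which these inputs do not reproduce. That is a separate matter. Only the effect size and group size are used below, and 91.8% is the baseline.

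**2. Visits side by side.**

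| Place | VSS time points |
|---|---|
| 7.1.2, endpoint definition | 7, 8 |
| 7.1.2, ANOVA and t-tests | two |
| 7.1.2, mixed model | 5, 6, 7, 8 |
| 6.2.2, weekly visits | none |
| 6.2.3 and Table 1 | 7, 8 |
| 6.5.5 | from closure onwards |

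On the schedule, Visits 5 and 6 hold no VSS data. Software that drops empty levels then fits the two-visit model. Scores can reach Visits 5 and 6 only through 6.5.5: directly for wounds closing at those visits, and for earlier closers only if the weekly LOCF is read as covering VSS.

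**3. Effect on the model-based t-tests if scores do enter.** A random subject effect plus a single residual variance implies the same total variance at every visit. With complete data the model's estimate is the average of the visit variances. Set the Visit 7 and 8 variance to 1, let s be the SD at Visits 5 and 6, and f the fraction of those cells filled (both assumed). Weighting visits by number of observations, which is approximate when f < 1:

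V = (2f·s² + 2)/(2f + 2); false-positive rate = 2[1 − Φ(1.96√V)].

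| f | s | V | Rate |
|---|---|---|---|
| 1 | 0.5 | 2.5/4 = 0.625 | 12.1% |
| 1 | 1.5 | 6.5/4 = 1.625 | 1.2% |
| 0.7 | 0.5 | 2.35/3.4 = 0.691 | 10.3% |
| 0.7 | 1.5 | 5.15/3.4 = 1.515 | 1.6% |
| 0.2 | 0.5 | 2.1/2.4 = 0.875 | 6.7% |
| 0.2 | 1.5 | 2.9/2.4 = 1.208 | 3.1% |

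At s = 1 the rate is 5%. A simulation of the model under no effect (40 per arm, 70% fill, 400 runs per scenario, Monte Carlo error about 1 point) gave 10.0–11.5% at s = 0.5, 1.5–2.2% at s = 1.5, and 5.5–6.0% with Visits 5 and 6 empty. Separate ANOVAs at Visits 7 and 8 do not use the other visits and stayed at 3.8–7.0% throughout.

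**4. Early-termination timing.** The Day 180 window opens on Day 180 − 14 = Day 166. With Visit 7 on Day 90, an exit on Day 91 is analysed as Day 180: 180 − 91 = 89 days early and 166 − 91 = 75 days before the window. For Day 90, a score must exist before Visit 7. Section 6.3.1 has leavers complete the procedures of the visit at which they leave, and weekly visits include no VSS, so this needs scoring at closure under 6.5.5. In that case a wound closed at Visit 2 on Day 5 could count as Day 90, 90 − 5 = 85 days early.

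**5. Early-termination effect on power.** Assume k of 40 per arm are moved and show no treatment difference yet. Moved: effect 0.75(40 − k)/40 at SE 0.2236. Left missing: effect 0.75 at SE √(2/(40 − k)).

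| k | Effect if moved | Power | SE if missing | Power |
|---|---|---|---|---|
| 1 | 0.731 | 90.5% | 0.226 | 91.2% |
| 2 | 0.7125 | 89.0% | 0.229 | 90.5% |
| 4 | 0.675 | 85.5% | 0.236 | 88.9% |

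**6. Two visits each tested at 0.05.** Chance of at least one false positive = 1 − P(|Z₁| < 1.96 and |Z₂| < 1.96). For assumed between-visit correlations of 0.4, 0.6 and 0.8 this is 9.3%, 8.8% and 7.8%.

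**The case against.** The best defence is that the schedule governs. Section 6.2.2 and Table 1 collect no VSS at Visits 5 and 6, so the two extra levels are empty and drop out. The carry-forward rule gives a rationale about wound healing, not scars. This stands, and it is why the listing is harmless on the schedule as written. It does not dispose of the point, because 6.5.5 says something different and nothing in 7.1.2 excludes a closure-day score.

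It is also fair that the Day 90 result is not clearly exposed to the early-termination rule, and that the loss is small: 0.7, 1.5 or 3.4 power points (91.2 − 90.5, 90.5 − 89.0, 88.9 − 85.5). Both hold.

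A reader might infer that the four-visit model dilutes the treatment effect by averaging it over visits with immature scars. The plan does not support that: it takes effects at each of two time points and names no pooled four-visit test. A reader might also infer that the two visit tests must have a fixed order. Both are named in advance as secondary, with results planned for each, and the three primary outcomes in 7.1.1 carry no multiplicity rule either. Ordering is therefore a trade-off for the sponsor, not a defect to be corrected.

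**Conclusion.** The point holds as an inconsistency within 7.1.2 and with the visit schedule, and as a missing window in the early-termination rule. Severity is minor.

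The per-visit ANOVAs, read as separate analyses, are unaffected by the visit list in every case. The model-based t-tests are unaffected only if Visits 5 and 6 are empty or their scores have the same spread as those at Visits 7 and 8. Otherwise the error rate can move in either direction. The 10–12% and 1–2% figures rest on assumed SD ratios of 0.5 and 1.5 and on 70% to 100% fill. At 20% fill, closer to what might occur without carry-forward, the rates are about 7% and 3%. The documents give neither the SDs nor the fill, so these figures illustrate the mechanism and do not predict a result.

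The early-termination rule clearly reaches the Day 180 result, and the Day 90 result only if VSS is scored before Visit 7. The power cost assumes 1 to 4 leavers per arm with no difference yet in their scars.

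**What to change.** In Section 7.1.2:

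- Replace the four-visit list with two visits, 7 and 8.
- State that any score taken at closure is kept out of this model, and that the weekly-visit LOCF of Section 7.1 does not apply to the scar scale.
- Use an early-termination score only if it was taken within ±2 weeks of Day 90 or Day 180. Otherwise treat it as missing in the mixed model and list it.

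Reconcile Section 6.5.5 with Sections 6.2.2 and 6.2.3 and Table 1 on when the scale is first scored. Optionally, add one sentence saying whether the two visit tests are ordered or descriptive.

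The cost is wording only, with no new visits or data. The downside is that a few out-of-window or closure-day scores are listed instead of modelled.

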6.2 VISITS AND EXAMINATIONS

6.2.1 Visit 1 – Presentation for Evaluation and Treatment

- 1. Explain the purpose and nature of the study, and have the subject or the subject's legally authorized representative **read**, **sign**, and **date** the IRB-approved informed consent document. In addition, the informed consent document must be signed and dated by the individual who consents the subject. Provide a photocopy of the signed informed consent document to the subject or subject representative, and place the original signed document in the subject's medical record. If the subject is unable to read or sign the informed consent, unable to comprehend the information provided in the consent process, or is younger than the legal age of consent, the parents, legal guardian, decision making proxy or next of kin must provide written consent, and the subject must provide assent as required by the IRB.
- 2. Determine the etiology, extent (TBSA), age (date of burn and number of hours since burn), burn depth, burn wound perfusion measurement with laser Doppler, and location of the burn. Use the provided figure for estimation of TBSA (Appendix 13).
 - If there are multiple burn wounds on a subject, the TBSA for all burn wounds combined must be <10%. Each burn wound must meet study criteria, only the data from the largest burn wound ("target wound") will be recorded in the case report forms and utilized for data analysis. If two or more burn wounds are within 1 cm of each other, the burn wounds can be evaluated as if they were a single burn wound.
- 3. Photograph the burn per standard of care.
- 4. Determine the Fitzpatrick skin type (refer to Section 13).
- 5. Obtain demographic information and medical history, including information on all concomitant medications.
- 6. Perform any required procedures for standard burn care (e.g., debridement, pain relief, tetanus vaccination).

- 7. Obtain baseline measures of the burn wound bed, including the area (in cm²) of the target wound. These measures include exudate type and amount, odor, presence of eschar, presence of epithelial islands, epithelialization of the burn, peri-burn skin characteristics, pain, itching, and state of the burn wound (must be "open"). Refer to Section 13 for details.
- 8. If the subject meets all of the inclusion criteria, the subject should be randomized.
 If the subject does not meet all of the inclusion, the subject will be considered a screen failure.

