7.1.1 Primary Efficacy

The primary objectives of the study include the proportion of subjects with the burn wound healed after 3 weeks of treatment, time (in weeks) to healing, and incidence of burn wound infection.,

Both the proportion of subjects with burn wound healed after 3 weeks of treatment and the time to heal between the two treatment groups will be analyzed using ANOVA. Also, the proportion of burn wounds healed at each of the 5 assessments (visit 2,3,4,5, and 6) between the two treatment groups will be analyzed through a mixed-effect ANOVA. The incidence of burn wound infection observed over the study will be compared between the two treatment groups, using a t-test.

The analysis of the primary efficacy evaluations will be performed for the ITT population.

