7.1.3 Exploratory Efficacy

Burn wound status (closed or open) at each study visit will be compared between the two treatments, using ANOVA for the combination groups of the burn wound perfusion and Fitzpatrick skin type.

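### The VSS model and the primary healing analyses name no baseline covariate, although perfusion and skin type are recorded before randomisation; naming them is a cheap, conditional gain in precision

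*Combined protocol and SAP*

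**What the plan says.** Section 7.1.2 models the VSS total score with treatment and assessment time point "as well as their interaction as fixed effects, and subject as a random effect". In Section 7.1.1 the proportion with the "burn wound healed after 3 weeks of treatment and the time to heal between the two treatment groups will be analyzed using ANOVA". Healed status over Visits 2 to 6 gets a mixed-effect ANOVA. None of these names a baseline covariate. The general text of Section 7.1 says that comparisons from ANOVA and/or "analysis of covariance (ANCOVA) models will be based on Type III sums of squares", but ties ANCOVA to no endpoint and no covariate.

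At Visit 1 (Section 6.2.1), step 2 records "burn depth, burn wound perfusion measurement with laser Doppler, and location of the burn". Step 4 is "Determine the Fitzpatrick skin type (refer to Section 13"). Randomisation comes only at step 8: "If the subject meets all of the inclusion criteria, the subject should be randomized". The table in Section 12 labels laser Doppler as the determination of burn depth.

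Both measures enter one planned analysis. Section 7.1.3 compares open or closed status at each visit "using ANOVA for the combination groups of the burn wound perfusion and Fitzpatrick skin type", as exploratory.

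**The concern.** The documents themselves give reasons to expect these two measures to matter. The chart in Section 13.1.2 grades scarring risk upward across the Fitzpatrick types. Section 2.1 relates burn depth to healing time and says that second degree burns can scar, and Section 5.2 admits burns up to deep partial thickness. Section 8 expects a larger variance than in the earlier dermatome study, because injuries are non-uniform and on different people. Section 6.1 describes 1:1 assignment and no stratification.

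So neither the design nor the main analyses use two recorded sources of variation in a trial of 80 subjects. If perfusion and skin type predict outcome, the confidence intervals for VSS and healing will be wider than the collected data require.

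**Working it through.** **Inputs from the documents (Section 8).** 40 per group, two-sided 5%, standardised effect 0.750, stated power about 70%, two-sample t-test.

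**Assumptions.** No R², SD or healing rate is given. R² is varied from 0 to 40%. It is the share of within-group outcome variance explained by all the covariates in the model together.

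**The plan's own figure.** The noncentrality is d·√(40/2) = 4.472d, on 78 degrees of freedom. For d = 0.750 it is 3.354 and power is 91.2%, not 70%. Power of 70% needs d of about 0.56 (noncentrality 2.504, power 69.6%). That mismatch is a separate matter; both effect sizes are carried below.

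**VSS at a single visit, q covariates.** The variance of the treatment difference is multiplied by F = (1 − R²)·77/(77 − q). The second factor is the cost of chance imbalance. The test has 78 − q degrees of freedom, and the noncentrality is 4.472d/√F. With q = 2 (perfusion and one ordered skin-type term), 77/75 = 1.027:

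| R² | F | SE ratio √F | Equivalent subjects 80/F | Power, d = 0.56 | Power, d = 0.750 |
|---|---|---|---|---|---|
| unadjusted | 1 | 1 | 80 | 69.6% | 91.2% |
| 0 | 1.027 | 1.013 | 78 | 68.5% | 90.5% |
| 10% | 0.924 | 0.961 | 87 | 73.0% | 93.1% |
| 20% | 0.821 | 0.906 | 97 | 77.9% | 95.5% |
| 30% | 0.719 | 0.848 | 111 | 83.1% | 97.4% |
| 40% | 0.616 | 0.785 | 130 | 88.3% | 98.8% |

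Simulation (40,000 trials per cell) gave 68.3, 72.9, 77.9, 83.0 and 87.9% at 0.56, and 90.6, 93.0, 95.5, 97.4 and 98.8% at 0.750.

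**Break-even.** F = 1 when R² = q/77. That is 2.6% for two terms, 1.3% for perfusion alone, and 7.8% if skin type enters as five indicators beside perfusion (q = 6). Hence one ordered term for skin type.

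**Area and age as well (q = 4).** At d = 0.56 the same formula gives 67.2, 71.8, 76.8, 82.0 and 87.4%. At equal R² this is about 1 point below two covariates throughout.

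**Time to healing, planned ANOVA plus perfusion.** Simulated with weekly visits, lognormal times (sigma 0.5), wounds unhealed at Visit 6 scored as 6, and 60% or 80% of controls healed by week 3; all of these are assumptions. From 70%, power goes to 73–74, 77–78, 82 and 86–87% at R² of 10, 20, 30 and 40% on the log-time scale. At R² of zero the loss is under 1 point.

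**Healed at Day 21, linear model on 0/1 plus perfusion.** Dichotomising discards part of the association. For a normal latent scale the usable share of R² is φ(z)²/[p(1 − p)], where p is the proportion healed and z its normal quantile. At p = 50% this is 0.1592/0.25 = 0.64; at 80% it is 0.49 and at 90% it is 0.34. Simulated power (R² on a latent logistic scale, 12,000 trials per cell, healing rates assumed):

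| Healed, control v Santyl | R² = 0 | R² = 20% | R² = 40% |
|---|---|---|---|
| 50 v 77% | 71.7 → 71.4% | 71.9 → 77.8% | 72.4 → 83.6% |
| 60 v 85% | 72.1 → 72.0% | 72.1 → 77.0% | 71.7 → 82.1% |
| 70 v 92% | 75.1 → 73.9% | 74.9 → 77.8% | 74.1 → 81.2% |
| 80 v 90% | 24.7 → 23.6% | 24.7 → 24.9% | 25.1 → 27.2% |

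**Type I error.** Adjusted tests stayed at 4.8–5.1% for time to healing and 4.7–5.5% for Day 21. For VSS, checked with four covariates, it was 4.8–5.2%.

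**The case against.** The strongest reply is that nothing here is wrong. An unadjusted comparison of randomised groups is a legitimate pre-specified choice, and every gain above rests on an R² that the documents do not supply. For perfusion alone, an R² of 20% needs a correlation of about 0.45 (√0.20) and 40% about 0.63 (√0.40). At the plan's own effect of 0.750 an R² of 10% adds only about 2 points. All of this stands. It limits the point to a recommendation.

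The prognostic evidence is also thinner than it looks. The healing times in Section 2.1 contrast first with second degree burns, while the synopsis defines the population as partial thickness. So the text supports depth as prognostic within this population only indirectly. Section 6.2.1 lists burn depth and perfusion as separate items, and only the Section 12 table equates them. This also stands. Against it, Section 7.1.3 shows that the planners thought both measures worth using, and the loss if they are not prognostic is about 1 point.

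A reader might infer that every baseline measure should be added, since step 7 of Visit 1 also says "Obtain baseline measures of the burn wound bed, including the area" and age is known. The documents do not support that. Section 2.1 names burned area and age only as severity classifiers, and no section links them to healing or scarring.

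A reader might also infer that, in an unblinded trial with loose ANCOVA wording, covariates would be picked after outcomes are seen. Nothing says so: Sections 7.1.1 and 7.1.2 specify unadjusted models.

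**Conclusion.** The point holds as a missed efficiency. It should not be read as bias, as an invalid analysis or as an inflated error rate; the planned comparisons are sound in this respect.

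The gain is clearest for VSS and time to healing, where an R² of 20% is worth about 8 points of power from a base of 70%. For VSS at 0.750 it is worth about 4 points, from 91%. Healed at Day 21 gains less, and its open/closed status is already examined by perfusion and skin type as exploratory.

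These sizes depend on the assumed R², on assumed healing rates and times for the healing endpoints, and, for VSS, on a single-visit comparison instead of the full mixed model. The change is worth making because the possible loss is about 1 point and the data are already collected.

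**What to change.** Before any outcome analysis, amend the statistical section as follows.

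- **Section 7.1.2:** add perfusion and Fitzpatrick type (one ordered term) as fixed effects in the VSS model.
- **Section 7.1.1:** add perfusion alone to the planned analyses of healed at Day 21 and time to healing. In the Day 21 linear model the treatment coefficient is then a covariate-adjusted risk difference.
- **Perfusion:** define one summary value for the target wound. Section 6.5.4 gives none, and Section 7.1.3 needs one anyway.
- **Missing baseline readings:** replace them by the mean over both groups.
- **Sensitivity analyses:** keep the unadjusted results.
- **Not to add:** target wound area and age.

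Whether ANOVA suits time to healing is a separate question; if that method changes, carry perfusion over to its replacement.

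The cost is wording only, with no new data. It uses two degrees of freedom in the VSS model and one in each healing model. If the covariates prove unrelated to outcome, about 1 point of power is lost for VSS and at most about 1 for the healing endpoints.
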